6b Choice of Comparator: Control participants will receive placebo capsules containing 288 mg of rice protein (California Natural Products, Lathrop, CA), 109.3 mg microcrystalline cellulose (Stauber USA, Fullerton, CA), 4.3 mg Aerosil® 200 fumed silica (Vivion Inc., San Carlos, CA), and 4.3 mg magnesium stearate (Nitika Pharmaceutical Specialties, Maharashtra, India), and formulated into a capsule by Metagenics, Inc. (Gig Harbor, WA).

7 Objectives

A methodological limitation of assessing the efficacy of CD treatments is that the gut microbiome of CD subjects is highly personalized in terms of state and dynamics. By correlating time-resolved fluctuations in the gut microbiome of CD subjects with their concomitant changes in the profile of XN metabolites, BA profiles, and other markers of gut microbiome-associated biochemical activity as well as with established surrogate end-points of the disease, we hypothesize:

1) XN at the given dose will be safe and tolerable in adults with active CD;

2) XN will improve biomarkers and improve the Crohn's Disease Activity Index (CDAI) an activity index of CD activity;

3) We can identify a biological signature(s) of XN through its metabolic byproducts in blood, urine, and stool as well as its effect on bile acid reabsorption; and

4) Specific biological signature(s) of XN exposure will uniquely contribute to changes in CD-associated disease activity indices.

To test these hypotheses and generate a conceptual model, we define four Specific Aims:

Protocol

- Aim 1. Determine the clinical safety and tolerability of xanthohumol in adults diagnosed with CD. We will determine the safety and tolerability of xanthohumol in adults diagnosed with CD over 8 weeks in a Phase 2 trial. The primary hypothesis is that in the XN arm, the number of participants with an adverse event or abnormal lab value will not be more than 50% higher than the number in the placebo group.
- Aim 2. Assess changes in levels of inflammation and symptom severity related to CD.

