Data on adherence to the treatment protocol will be assessed qualitatively and quantitatively by asking participants if they have missed any doses, and why doses were missed if relevant, during each bi-weekly visit, plus by pill count at the week 4 and week 8 clinical visits by the Study Coordinator. A limited supply of product, adequate for 5 weeks, will be dispensed at the Randomization visit and at the Week 4 clinical visit.

11d Permitted concomitant care or intervention during trial

- Anti-inflammatory medications including oral 5-aminosalicylates (e.g., sulfasalazine, mesalamine)
- Immunomodulators (e.g. azathioprine, 6-mercaptopurine, methotrexate)
- Use of over-the-counter medications as indicated on the label for less than 2 days per week
- Multi-vitamin and/mineral
- Dietary supplements except as detailed below

Allowed emergency intervention during trial

• Glucocorticoids (e.g., prednisone, budesonide)

Prohibited concomitant care during trial

- Dietary supplements containing xanthohumol
- Dietary supplements containing flavonoids
- Other known "anti-inflammatories" including curcumin, turmeric, fenugreek, hops, rosemary, ginger, white willow, devil's claw, fish oil (doses>1 g/day), or quercetin.
- Anti-coagulant or anti-platelet prescription medications
- Antibiotic, antiparasitic, or antifungal medications orally or intravenously

12 Outcomes

Table	1
I HOIC	

OUTCOME	MEASURE	DESCRIPTION
Primary: Safety & Tolerab	ility	
Clinical Safety/Cumulative Toxicology	Liver (AST, ALT, GGT) and renal function (eGFR, BUN:Cr) tests plus hematology (CBC)	Routine clinical toxicology measures
Secondary: Clinical Status		
Gut inflammation	Fecal calprotectin	Enzyme-linked immunosorbent assay

Inflammation	Plasma pro-inflammatory	Flow cytometry-based multiplex assay
	cytokines (TNF-α, IL-1β,	C reactive protein from Quest Labs
	IL-2, IL-6, IL-8, IL-10,	C-reactive protein from Quest Labs
	and IL-12p70) and C-	
	reactive protein	
Composite Symptoms	Crohn's Disease Activity	Symptom severity will be determined
	Index (CDAI)	using the CDAI
Tertiary: Mechanistic Patl		
Metabolic byproducts of	XN and XN metabolites	Ultra-high-performance liquid
XN	in blood, urine and stool	chromatography-quadrupole time-of-
		flight mass spectrometry
Bile acid re-absorption	Bile acid concentrations	Ultra-high-performance liquid
	in blood and feces	chromatography-quadrupole time-of-
		flight mass spectrometry
Exploratory/Other	•	

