Gut integrity and	Plasma concentrations of	ELISA will be used to measure
enterocyte damage	soluble CD14, intestinal	soluble markers of microbial
	fatty acid-binding protein,	translocation from the intestine
	and lipopolysaccharide-	
	binding protein by ELISA	
	Plasma endotoxin by	Plasma endotoxin by Limulus
	Limulus amebocyte lysate	amebocyte lysate assay will measure
	assay	the microbial translocation
	TLR2, TLR4 activation	HEK293 cells pre-transfected with
	by transfected HEK293	TLR4 and TLR2
	reporter cells	
Lipid metabolism	Lipidomics profiling	Liquid chromatography UPLC-QTOF

Primary Outcome: Clinical Safety/Cumulative Toxicology

Standard clinical Complete Blood Counts and toxicology panels including liver and renal function tests will be measured at each bi-weekly clinical visit. Values will be interpreted based on: new abnormal value, change since baseline, new emergency or alert values, and/or the emergence of new diagnostic concerns. All participants' labs will be reviewed by a clinical investigator, and any abnormal lab values meeting halting criteria will be recorded in the database.

Should a participant experience a severe or emergent event: 1. The AE and its severity will be documented; 2. The participant's medical provider will be notified and consulted; and, if unavailable, 3. The DSMB Chair ([name], MD, PhD; Division Chief of General Surgery, OHSU) will be consulted if the study team is unable to reach the participant's physicians.

Secondary Outcome: Fecal Calprotectin

Levels of calprotectin, a marker of CD, will be determined in stool samples using a commercial ELISA kit.

Secondary Outcome: Inflammatory markers

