A sample size of 12 per group provides 80% power to detect a 50% difference in proportions of participants between groups by chi2 test experiencing a laboratory abnormality or adverse event at a significance threshold of α =0.05. In addition, based on our preliminary trial data for change in TNF- α , and applying a 2-sided t-test of means, n=24 allows for n=12 per arm and provides >90% power, at a significance threshold α =0.05, to detect a mean change of -0.5 =/- 0.25 pg/ml in XN-treated participants with CD, based on an estimated mean change of 0.1 +/- 0.25 pg/ml from placebo. Will we randomize up to 32 participants to allow for attrition up to 25% [resulting in a final sample of at least n=24/arm.

Based on our preliminary trial data for change in TNF- α , and applying a 2-sided t-test of means, n=24 allows for n=12 per arm and provides >90% power, at a significance threshold α =0.05, to detect a mean change of -0.5 =/- 0.25 pg/ml in XN-treated participants with CD, based on an estimated mean change of 0.1 +/- 0.25 pg/ml from placebo. Will we randomize up to 32 participants to allow for attrition up to 25% [though we had <10% attrition in our previous trial in this population] resulting in a final sample of at least n=24/arm.

15 Recruitment

Participants will be recruited from the region via posted fliers and the NUNM clinic via posted fliers and IRB-approved mailings to current patients. Members of the study team will present information about study participation to CD support and community groups and set out flyers for attendees to pick up. In addition, we will use Craigslist and social media (i.e. Facebook and Instagram) as well as the NUNM weekly newsletter. Candidates from the community would

simply respond to a dedicated study telephone line or email, and express their interest, and are then contacted by a Study Coordinator.

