Laboratory measures (including red blood cell count, white blood cell count, hematocrit (%), hemoglobin, mean corpuscular volume, AST, ALT, creatinine-estimated glomerular filtration rate (eGFR), blood urea nitrogen (BUN), and creatinine) will be analyzed by first assessing descriptive statistics including mean, median and standard deviation. All distributions will be tested for skew and transformed (e.g., natural log transformed) as needed to reduce the influence of skew in subsequent analyses. All parameters will be evaluated by formally comparing means from baseline

Protocol

to each time point by unpaired, 2-sided t-tests, as well as for trends over time by applying linear mixed ANOVA models with time point as a repeated factor.

As an element of the evaluation for safety of the intervention, the % laboratory newly abnormal (for values within the clinically normal range at baseline) per clinical laboratory reference ranges for each lab parameter will be reported at each 2-week time point and the % compared between XN and placebo groups by Fisher's exact test.

Assessment for changes in the distribution of each lab parameter will be performed by presenting means and confidence intervals (CI) for the change in each group, as well as the mean CI for the difference between groups; significance will be tested using 2-sided, unpaired t-tests (or, if inspection of distributions indicates strong non-normality, with a non-parametric Wilcoxon signed rank test) of the mean values for XN compared to placebo.

Assessment for overall *increases* or *decreases* in parameters of interest will be tested for linear trends of the means by linear mixed ANOVA with time point as a repeated factor, which may be suggestive of evidence for cumulative toxicity if trending in a clinical deleterious direction.

Analysis of inflammatory cytokines, gut permeability biomarkers, and endotoxemia:

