The PI will have final responsibility for all reporting to the NUNM IRB, DSMB and/or NCCIH PO as required.

Clinical Management Plan/ Plans for Ensuring Necessary Medical Intervention

Participant safety is of the greatest concern in clinical trials of experimental compounds, even when naturally derived and available in food. Of particular concern is any threat to the clinical stability of a person with CD. For this reason, with their consent, we will notify participant's primary care and/or medical specialist of their patient's participation in the trial. We will inform their medical providers should it become necessary to communicate with them about any laboratory abnormalities, critical values and/or AEs should they be discovered at baseline or throughout the clinical trial.

We will maintain the ability to administer additional blood-based or stool-based testing for acute or viral infection as circumstances require.

Potential Risks to Participants

Risks associated with any dietary supplement include gastrointestinal symptoms such as gas, bloating, digestive upset and change in bowel movement frequency or consistency. Also, there is a chance of identifying a previously unknown allergy, and therefore a risk of rash, breathing difficulty and serious allergic reaction.

We will ask about symptoms at each study visit and any side effects will be recorded. We may ask the participant to discontinue the study product if we believe it would be in their best interest.

There will be six blood draws during this study. There is a small chance that the needle will cause some discomfort, bruising, redness or bleeding at the needle puncture site. Occasionally, individuals may feel lightheaded or faint during or immediately after a blood sample is collected. There is a rare risk of swelling around the vein or of infection.

We will do everything we can to keep records private, yet there is always a small risk of a breach of confidentiality of personal health information. These risks have been addressed and minimized as much as is possible by keeping data in locked cabinets and on password protected and encrypted computers, and by using ID numbers instead of names on all data collected.

There is a chance that some participants may confuse research study visits for routine clinical care. **Protocol** Study Title: Xanthohumol Microbiome and Signature in Crohn's Disease (XMaS in Crohn's) Trial

23 Auditing

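### The primary safety outcome is an adverse-event-or-laboratory composite in Aim 1 and section 14 but laboratory tests only in Table 1 and section 12, and section 20a does not analyse the composite

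*Protocol*

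**What the plan says.** Section 7, Aim 1, frames the primary hypothesis per participant. What it counts is "the number of participants with an adverse event or abnormal lab value". The hypothesis is that this count in the xanthohumol arm "will not be more than 50% higher than the number in the placebo" arm. Section 14 sizes the trial by chi-square test: "A sample size of 12 per group provides 80% power to detect a 50% difference in proportions". The event is the same composite, since the people compared are those "experiencing a laboratory abnormality or adverse event at a significance threshold of" 0.05.

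Section 12, Table 1, heads its first block as primary, safety and tolerability. Its only measure is "Liver (AST, ALT, GGT) and renal function (eGFR, BUN:Cr) tests plus hematology (CBC"). The text headed Primary Outcome: Clinical Safety/Cumulative Toxicology also concerns laboratory panels only. It lists four bases for interpreting a value, the first being a new abnormal value. It then says that a clinical investigator reviews the results and that "any abnormal lab values meeting halting criteria will be recorded in the database". Adverse events appear there only in the steps to follow after a severe or emergent event.

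Section 20a, under laboratory toxicology measures, takes values that were normal at baseline. The percentage newly abnormal "per clinical laboratory reference ranges for each lab parameter will be reported at each 2-week time point" and is compared between groups by Fisher's exact test. Section 20a describes no analysis of adverse events.

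**The concern.** The primary outcome is what the trial is sized on and what its conclusion will be read against. Here two parts of the protocol include adverse events in it and two leave them out. A team following Table 1, section 12 and section 20a as written would not test the hypothesis stated in Aim 1.

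The part left out is not minor. Section 22 says: "Risks associated with any dietary supplement include gastrointestinal symptoms such as gas, bloating, digestive upset and change in bowel movement frequency or consistency". These are the first risks the protocol names, and they are reported as symptoms; the primary row of Table 1 holds only liver, renal and blood-count tests.

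With at most 32 participants, a few events either way can change the comparison. If the definition is still open when results are seen, the choice between the two could be influenced by them.

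**Working it through.** **1. The plan's own figure.** Section 14 gives 80% power with 12 per group, a 50% difference in proportions, chi-square and α = 0.05. It gives no placebo rate. With placebo rate p0, active rate p1, their mean p̄ and n per group:

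power = Φ{ [ |p1 − p0|·√n − 1.96·√(2p̄(1 − p̄)) ] / √(p0(1 − p0) + p1(1 − p1)) }

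Taking the 50% as percentage points (an assumption) and p0 = 5%, p1 = 55%, n = 12: p̄ = 0.30; numerator 0.5 × 3.464 − 1.96 × 0.648 = 0.462; denominator √(0.0475 + 0.2475) = 0.543; ratio 0.850; power 80.2%. The stated figure is reproduced there, but not at every rate:

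| Assumed placebo vs active | Power, 12 per group |
|---|---|
| 1% vs 51% | 84% |
| 5% vs 55% | 80% |
| 10% vs 60% | 76% |
| 25% vs 75% | 71% |

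Aim 1 words the 50% as a relative excess. On that reading the same formula gives 5.5% (10% vs 15%), 24% (50% vs 75%) and 39% (60% vs 90%). Which reading is meant is a separate question. On either one, the figure depends on a placebo rate that the protocol does not state.

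**2. Who counts as an event.** Four kinds of participant, judged by each section, using the same rule for an abnormal laboratory value throughout:

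| Participant | Aim 1, section 14 | Table 1, section 12 |
|---|---|---|
| Adverse event, labs normal | event | not an event |
| No adverse event, newly abnormal lab | event | event |
| Both | event | event |
| Neither | not an event | not an event |

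The definitions disagree on the first row. Every laboratory-only event is also a composite event, so the composite rate is at least as high as the laboratory-only rate. It is higher by the share of participants with an adverse event and normal laboratory values. The protocol gives no figure for that share, so the gap cannot be sized.

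**3. What section 20a tests.** It names 10 laboratory measures (red and white cell counts, hematocrit, hemoglobin, mean corpuscular volume, AST, ALT, eGFR, BUN and creatinine). There are four post-baseline visits (weeks 2, 4, 6 and 8). That gives at least 10 × 4 = 40 parameter-by-visit comparisons of the percentage newly abnormal. None is a count of participants with any event, and none includes adverse events. The only test named for the composite is the chi-square in section 14, as a basis for power.

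**The case against.** The strongest reply is that adverse events are plainly part of the safety evaluation. Section 11b puts self-reported adverse events first among the safety measures, the multi-system questionnaire is given at every bi-weekly visit (section 18a), and the trial halting rule in section 21b counts adverse events. Table 1 is headed safety and tolerability, and a statistical analysis plan not shown here may contain the composite analysis. This disposes of one inference a reader might draw, that tolerability could be declared without being measured. It is measured. What remains is whether it counts in the primary outcome; an analysis plan would still have to choose between two definitions in the protocol.

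A reader might also infer that section 12 and section 20a set contradictory laboratory thresholds: halting criteria in one, the reference range in the other. The text does not support that. The halting-criteria sentence says what is recorded after clinical review and does not define an event. The sentence before it lists a new abnormal value first, which agrees with sections 11b and 20a. Section 19 already sends all visit data to case report forms and REDCap. Nor can halting criteria be assumed to exclude mild abnormalities, since one of the two Phase 1 values that met them was a mild anemia (section 6a). The sentence is loosely placed, and the protocol gives no laboratory cut-offs for it, so it needs clarifying.

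A third inference would be that a reference-range rule makes most untreated participants events, so that the contrast in section 14 cannot occur. That requires out-of-range rates the documents do not give, and an any-parameter, any-visit event that section 20a does not define. No such figure is offered here.

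**Conclusion.** The point holds as a contradiction between definitions. The protocol has two primary safety outcomes, which classify a participant with an adverse event and normal laboratory values in opposite ways. The stated primary hypothesis has no matching analysis in section 20a.

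This conclusion rests on the text alone and needs no assumed rate. The power figures have a narrower use. They show that section 14's 80% is attainable, at about 5% versus 55% on the absolute reading, but cannot be confirmed until the event is fixed and its placebo rate stated. They do not show that the figure is wrong. The correction should be made before investigators are unmasked.

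**What to change.** - Use one per-participant primary event in Aim 1, Table 1, section 12, section 14 and section 20a: an adverse event or a newly abnormal laboratory value. Add adverse events to the primary row of Table 1 and to the primary-outcome text of section 12.
- Add the between-group comparison of that composite to section 20a, and keep the per-parameter, per-visit tables as supporting analyses.
- State in section 14 the placebo rate assumed for this event, and restate the power if it changes.
- Say in section 12 that the halting-criteria sentence is a recording or flagging rule and not the event definition, and reconcile it with the newly-abnormal wording in sections 11b and 20a. Any clinical cut-off is for the investigators to set.

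The cost is wording and one extra comparison. Adverse events and laboratory values are already collected at each bi-weekly visit, so no visit or assay is added. The restated power may be less favourable than 80%.

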Exploratory Outcome: Circulating Endotoxin

As an additional measure of gut integrity, levels of lipopolysaccharide (endotoxin), a component of Gram-negative bacteria, will be determined with the Limulus amoebocyte assay. The version of the assay used in this study will be a microplate-based chromogenic, endpoint assay.

Exploratory Outcome: Bacterial Translocation

Bacterial translocation out of the gut lumen will be measured by TLR2 and TLR4 activation. The proposed reporter-cell assay uses cultured HEK293 cells that have been transfected with a chimeric protein consisting of the extracellular portion of the TLR2 or TLR4 receptor, conjugated with a truncated placental alkaline phosphatase enzyme. Ligand binding to the receptor initiates the production of a colored metabolite which can be quantified in a spectrophotometer.

Exploratory Outcome: Lipidomics

As an additional component of the biological signature of XN in CD, lipidomic analysis will be performed by UPLC-QTOF. These data will be combined with the results of XN metabolite and bile acid profiles in modeling the biological signature.

13 Participant timeline:

Table 2							
	Phone Screening	Clinical Screening	Baseline Clinical Visit - Week 0	Randomization Visit – within 48hrs after Baseline	Bi-weekly Clinical Visits (Weeks 2,6)	Midpoint Clinical Visit- Week 4	Trial Closeout- Week 8
Oral waiver of consent	Х						
Initial eligibility screening	Х						
Written informed consent		X	Х				
W9 Form		Х					
Written release of medical records				X			
Demographics		Х					
Randomization				Х			
Assessment of Symptoms/AEs			Х		Х	Х	X
PROMIS-29			Х		Х	Х	Х
Disease Activity scale (CDAI)	Х	Х	Х		Х	Х	X

Protocol

	KESEAR		IUIE		Template Version	n 02.02.17
Adherence assessment (verbal recall)				Х	Х	Х
Adherence						
assessment					Х	Х
(pill count)						
Labs: CBC, &						
Toxicology	Х	Х		Х	Х	Х
Panel (Chem 13), CRP	71	7		1	7	~~~~~~~~~~~~~~~~~~~~~~~~~~~~~~~~~~~~~~~
Blood collection	Х	Х		Х	Х	Х
Urine collection			Х	Х	Х	Х
Stool collection			Х	Х	Х	Х
XN or placebo dispensed			Х		Х	
Stipend ordered					Х	Х
Participant Discharged						Х

13b Missed visits

In the case of an inability to conduct study visits as intended the study team will move forward with the following procedures according to the circumstantial requirements.

1. Participants refuse or are unable to come in for a Week 2 or Week 6 (Interim) visit: Study Procedures:

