a. Request the participant drop off stool and urine samples outside the building in the sample dropbox or ship the samples to the study site using a sample shipment kit sent by the study team

b. Participants will complete surveys and AE questionnaires electronically via REDCap and over the phone with Coordinators. CDAI will be filled out to the greatest extent possible virtually.

c. Study team will assess the participants willingness to go to a remote Quest facility for a blood draw

2. Participants refuse or are unable to come in for a Week 4 (Midpoint) visit: Study Procedures:

Study Procedures:

- a. Follow number 1 study procedures with the addition of:
 - i. Request the participant keep all unused product and drop it off in the outside sample drop box or ship the samples to the study site using a shipment kit sent by the study team

Protocol

ii. Participant will be mailed their 2nd and last allotment of study product

- 3. Participants refuse or are unable to come in for a Week 8 (Closeout) visit:
 - Study Procedures:
 - a. Follow number 2 study procedures with the exception of:
 - i. Study product dispensation
 - ii. Incentive to go to a Quest draw site will be increased to \$200.00 as necessary
- 4. Provisional research institute closure:

Study Procedures:

- a. Participants will be informed to continue taking their assigned study product until they reach their Week 8 time point
- b. Participants will not attend any interim visits
- c. New study product will be mailed to participants if the week 4 visit is attained and institute remains closed
- d. If institute closure persists for scheduled participant closeout visit, participant will be informed to discontinue study product at the end of Week 8, final surveys and AE interviews will be completed remotely. CDAI will be filled out to the greatest extent possible virtually. Incentives to go to a Quest draw site will be increased to \$200.00.

14 Sample Size

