We will also recruit via targeted clinical recruitment in the EPIC electronic health records system by working with an internal EPIC specialist to create a list of candidate participants based on ICD-9/10 codes from NUNM electronic health records. Similarly, our OHSU collaborator will use the Data Warehouse resource of the Oregon Clinical and Translational Research Institute (OCTRI) to identify potential candidates from OHSU's EPIC database. Upon creation of a candidate list, IRB-approved study materials, i.e., an invitation letter and a copy of the flyer, will be mailed to them. They will not be re-contacted if they do not respond to an initial invitation. We will present at medical conferences and have flyers available for conference participants. Additional retention strategies include the use of stipends dispensed for clinical screening (\$50) and each clinical visit completed (\$190 each) following enrollment for up to a total of \$1,000. Additional compensation (\$200) will be provided in the event that closure of campus (e.g. due to COVID-19) requires the participant to go to Quest Diagnostics' phlebotomy clinic for their required blood draw. Participants may be reimbursed for travel and/or lodging expenses if travel cost is a barrier to participation.

Planned						
Table 3 Racial			Ethnic Categorie	S		
Categories	Not Hispanic o		 	Hispanic or Latino		
	Female	Male	Female	Male		
American	0	0	0	0	0	
Indian/Alaska						
Native						
Asian	1	1	0	0	2	
Native	0	0	0	0	0	
Hawaiian or						
Other Pacific						
Islander						
Black or	2	2	1	1	6	
African						
American						
White	11	10	2	1	24	
Total	14	13	3	2	32	

Inclusion Enrollment

This study will enroll biologically male and female participants and therefore will include women. We aim to recruit a sample that is 50% male and 50% female in order to maximize the generalizability of our findings to both men and women. Furthermore, Inflammatory Bowel Disease (IBD) is more common in females (relative risk: 1.53 compared to males) and therefore we are confident women will be well represented.

Protocol

This study will recruit generally from the Oregon and Washington region. Based on the 2016 census, the ethnic distribution of the Portland, OR area is: Caucasian 70%, Hispanic/Latino 10%, Asian 8%, Black 6%, Pacific Islander 1%, Native American 0%, and Other 0%. Participants who come from beyond the immediate area may be compensated for travel and lodging expenses if it is a limiting factor.

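### During an institute closure, item 4 of section 13b continues dosing but states no safety labs, sample return or scheduled AE/CDAI contact between baseline and Week 8, unlike items 1 and 2 for an ordinary missed visit

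*Protocol*

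**What the plan says.** Section 13b of the protocol sets out four situations.

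- **Items 1 to 3, a participant who cannot attend.** For Week 2 or 6, stool and urine are dropped off or shipped, and the CDAI is completed remotely as far as possible. For AEs, "Participants will complete surveys and AE questionnaires electronically via REDCap and over the phone with Coordinators". For bloods, "Study team will assess the participants willingness to go to a remote Quest facility for a blood draw". Item 2 (Week 4) and item 3 (Week 8) each bring in the preceding item's procedures by express reference.
- **Item 4, institute closure.** On dosing, 4a states: "Participants will be informed to continue taking their assigned study product until they reach their Week 8 time point". On visits, 4b states: "Participants will not attend any interim visits". Under 4c, new product is mailed if Week 4 is reached while the institute is still closed. Under 4d, if closure lasts to closeout, final surveys and AE interviews are done remotely, the CDAI is completed virtually as far as possible, and a larger incentive is paid for a Quest draw.

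Elsewhere, section 12 makes the safety labs the primary outcome: "toxicology panels including liver and renal function tests will be measured at each bi-weekly clinical visit". Section 20a compares the percentage newly abnormal between arms at each two-week point. Section 11b withdraws a participant with a critical laboratory value. Section 15 pays \$200 if campus closure "requires the participant to go to Quest Diagnostics' phlebotomy clinic for their required blood draw", without saying which visits.

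**The concern.** A closure affects every participant on treatment at the time, yet item 4 specifies less safety data collection than items 1 and 2 do for one absent participant. Dosing goes on, and item 4 mails the second supply without the remote AE questionnaire, sample return and draw offer that item 2 attaches to the same mailing.

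Three parts of the plan depend on the missing data:

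- The lab comparison at each two-week point (section 20a) loses observations.
- Aim 1 (section 7) and the sample size (section 14) count participants with an AE or abnormal lab value. Fewer draws give fewer chances to be counted, in a trial whose primary hypothesis is that the product is safe.
- The critical-value withdrawal rule (section 11b) cannot operate on labs that are not drawn.

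**Working it through.** **1. The schedule.** Table 2 gives labs at screening, baseline and Weeks 2, 4, 6 and 8: 1 + 1 + 4 = 6 draws. This reproduces the six draws stated in section 22 under potential risks. Four of them are post-baseline.

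**2. The items side by side.**

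| | Items 1–2 (ordinary missed visit, Weeks 2, 4, 6) | Item 4 (closure, before Week 8) | Item 4d (closure, Week 8) |
|---|---|---|---|
| Safety bloods | Quest draw offered | none stated | Quest draw with incentive |
| AE contact | REDCap and phone | none stated | remote interview |
| CDAI | remote, as far as possible | none stated | remote, as far as possible |
| Stool and urine | drop-off or shipment | none stated | none stated |
| Product | mailed at Week 4 | continues; mailed at Week 4 | stops at end of Week 8 |

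**3. What counts as interim.** Item 1 reads: "Participants refuse or are unable to come in for a Week 2 or Week 6 (Interim) visit". Item 2 labels Week 4 the midpoint. On the narrow reading, 4b cancels Weeks 2 and 6 only, and a Week 4 draw might still be obtained, for example through item 2. On the broad reading, Week 4 is included, since item 4 states no Week 4 draw either.

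**4. Panels without a stated draw, per participant.** Assume that closure lasts to closeout and that the Week 8 draw is obtained.

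| Closure begins | Narrow (Weeks 2, 6) | Broad (Weeks 2, 4, 6) |
|---|---|---|
| before Week 2 | 2/4 = 50% | 3/4 = 75% |
| after Week 2 | 1/4 = 25% | 2/4 = 50% |
| after Week 4 | 1/4 = 25% | 1/4 = 25% |
| after Week 6 | 0 | 0 |

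**5. Trial-wide loss.** Loss = share of participants in closure throughout treatment × per-participant loss. The shares are assumptions; the protocol gives none.

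| Share fully affected | Narrow (× 0.50) | Broad (× 0.75) |
|---|---|---|
| 10% | 5.0% | 7.5% |
| 25% | 12.5% | 18.8% |
| 50% | 25.0% | 37.5% |

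On the broad reading the loss passes one half only if the share exceeds 0.50 / 0.75 = 67%. On the narrow reading it never exceeds 50%.

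**6. Chance of detecting any new lab abnormality.** Let q be the chance of an abnormal value at one draw (assumed). If draws were independent, the chance over k draws is 1 − (1 − q)^k.

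| q | k = 1 | k = 2 | k = 4 |
|---|---|---|---|
| 2% | 2.0% | 4.0% | 7.8% |
| 5% | 5.0% | 9.8% | 18.5% |
| 10% | 10.0% | 19.0% | 34.4% |

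The broad reading leaves k = 1 and the narrow reading k = 2. Independence is the unfavourable extreme. If a participant's results were perfectly correlated across visits, every column would equal q and nothing would be lost on this measure. Repeated labs in one person probably lie between the two.

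**The case against.** The strongest reply is that item 4 is silent rather than contradictory. The opening of 13b says that procedures follow the circumstances, and a closed institute plainly makes participants unable to come in, so items 1 and 2 might be taken to apply. Item 4b stops attendance; it does not forbid remote collection. This has some force, but items 2 and 3 import earlier procedures expressly and item 4 does not. Item 4d also writes out the remote steps for closeout, which would be unnecessary if items 1 to 3 already applied. Staff following item 4 as written would have no instruction to collect anything before Week 8.

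Other points stand and limit the concern:

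- Item 1 only asks about willingness to have a Quest draw, so an ordinary missed visit does not guarantee a lab result either.
- AEs can be reported spontaneously at any time (sections 18a and 22), so AE capture and AE-based withdrawal do not stop.
- Closure would affect both arms, and the section 20a test at each time point does not pool participants with different numbers of draws.

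A reader might go further in four ways that the protocol does not support:

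- *There are no remote labs in a closure.* Item 4d foresees a Quest draw at Week 8.
- *Most of the trial's primary safety data would be lost.* That needs the broad reading and more than two thirds of participants in closure throughout treatment.
- *Section 15 contradicts item 4.* Its payment names no visit and is compatible with the \$200 in 4d; it leaves open which draws are required.
- *Phase 1 shows that a Week 8 draw misses transient abnormalities.* The background section describes abnormalities present at Week 8 that resolved on re-testing, so a Week 8 draw had found them.

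**Conclusion.** The gap is real and worth closing, but it is contingent on a closure. For a participant in closure throughout treatment, 2 of 4 post-baseline panels (narrow reading, with a Week 4 draw obtained) to 3 of 4 (broad reading) have no stated draw. The loss falls to none if closure starts after Week 6. It would be larger if the Week 8 draw were declined, since that draw is encouraged but not assured. Scheduled AE and CDAI contact before closeout is likewise unstated.

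The trial-wide effect cannot be fixed from the protocol, because the share of participants affected is not given. The consequences are thinner bi-weekly primary safety data, a lower chance of counting a participant with any abnormal lab, and a critical-value withdrawal rule without results for part of the dosing period. The detection figures above show the direction of the effect; they rest on assumed per-draw rates and on independence.

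**What to change.** Reconcile item 4 of section 13b with items 1 to 3 and with the payment text in section 15. State in item 4 that the remote data-collection procedures already written also apply at Weeks 2, 4 and 6 during a closure: AE questionnaires by REDCap and phone, virtual CDAI, shipment of stool and urine, and the offer of a Quest draw. State whether interim in 4b includes Week 4, and which draws the section 15 payment covers.

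The cost is a short change of wording, extra Quest payments for the interim draws and participants' travel to a draw site. Payment for closure draws is already foreseen in section 15. Whether product continues when labs cannot be obtained is for the sponsor and DSMB to settle.
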